#### **14.2.3 Relationship of Adverse Events to Study Drug**

The Investigator will assess the potential relationship of the AE to study drug using the following descriptions.

- ***Not Related:*** This category applies to an AE that is clearly not related to the study drug beyond a reasonable doubt. That is, another cause of the event is most plausible; and/or a clinically plausible temporal sequence is inconsistent with the onset of the event and the administration of study drug and/or a causal relationship is considered biologically implausible.
- ***Unlikely Related:*** This category applies to an AE that could reasonably be considered caused by something else, and where there is no known or expected response pattern to the suspected study drug.
- ***Possibly Related:*** This category applies to an AE that follows a reasonable temporal sequence from administration of the study drug and that follows a known or expected response pattern to the suspected study drug, but that could readily have been produced by a number of other factors.
- ***Probably Related:*** This category applies to an AE that follows a reasonable temporal sequence from administration of study drug and that follows a known or expected response pattern to the suspected study drug. The AE could have been produced by a number of other factors, but the alternatives are not likely.
- ***Definitely Related:*** This category applies to an AE that is clearly related to study drug. The AE follows a clear temporal sequence from administration of study drug, follows a known or expected response pattern to the study drug, that is confirmed by improvement on stopping and reappearance of the event on repeated exposure and that could not be reasonably explained by the known characteristics of the subject's clinical state.

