### **8.6.1 Study Halting and Study Stopping Rules**

Dosing may be halted temporarily to investigate before the entire study is terminated. If any of the below events occur, enrollment and dosing should be halted study-wide pending review by the Sponsor, Investigator, and/or Medical Monitor. Subjects enrolled in the study must continue to be followed for the duration of the study.

- One or more subjects with a serious adverse event (SAE) considered definitely, probably, or possibly related to the IPs.
- Three or more subjects with the same or similar grade 3 or higher AEs of the same type considered definitely, probably, or possibly related to IPs.
- One AESI, considered at least possibly related to the IPs.

If any of these events occur, enrollment and dosing should be paused study-wide pending review by the Sponsor, Investigator, and/or Medical Monitor. Subjects enrolled in the study must continue to be followed for the duration of the study.

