#### 14.2.6 Adverse Events of Special Interest

In consideration of the limited safety data available on prior skin test studies, two specific AESIs have been identified:

- Anaphylactic reaction ([Appendix 4](#)).
- Enhanced disease from repeated exposure to SARS-CoV-2 (in subjects who have recovered from SARS-CoV-2 infection or in subjects recently vaccinated against SARS-CoV-2).

Adverse events of special interest are events of scientific and medical interest specific to the further understanding of the TNX-2100 skin test. Investigators are advised to monitor subjects carefully for potential development of these adverse events as well as other adverse events (eg. local site reaction) and are required to have the appropriate safety equipment on site (crash cart and adrenaline auto-injectors [EpiPen, Jext or Emerade]). All investigative site staff will be trained in

identifying anaphylaxis and a medically licensed professional trained in the clinical management of anaphylaxis will be present at the skin test administration visit (Visit 1, Day 1) for the duration of Stages 1 and 2. Investigators are required to communicate such events immediately to the Sponsor. An AESI can be serious or non-serious. All AESIs should be entered in the Electronic Data Capture (EDC) within 24 hours of reported onset and will be recorded in the CRF. Serious AESIs will be recorded and reported as per [Section 14.3.1](#).

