9.1. Adverse Events

Treatment emergent AEs are defined as AEs that either commenced following initiation of study treatment or was present prior to study treatment but increased in frequency or severity following initiation of study treatment. Adverse events of special interest (AESI) include anaphylactic reaction and enhanced disease from repeated exposure to SARS-CoV-2 (in subjects who have recovered from SARS-CoV-2 infection or in subjects recently vaccinated against SARS-CoV-2).

All AEs occurring after completion of the informed consent process and before the end of study, regardless of relationship to study drug, will be included and classified by system organ class (SOC) and preferred term (PT) using the Medical Dictionary for Regulatory Activities (MedDRA) v24.0.

For treatment-emergent AEs (TEAEs), the following will be summarized and presented for the Safety population:

An overall summary of TEAEs, which includes:

- a. the number and percentage of patients experiencing a TEAE
- b. the number and percentage of patients experiencing a TEAE by strongest relationship to IP
- c. the number and percentage of patients experiencing a TEAE by highest severity grade
- d. the number and percentage of patients experiencing a systemic allergic reaction by highest grade according to the World Allergy Organization Grading Scale for Systemic Allergy Reactions
- e. the number and percentage of patients experiencing a treatment emergent SAE (TESAE)
- f. the number and percentage of patients experiencing a TEAE leading to study discontinuation
- g. the number and percentage of patients experiencing a treatment emergent AE of Special Interest

In the overall summary of TEAEs table, besides tabulating the number and percentage of patients, the total number of TEAE episodes will also be provided. If a patient has repeated episodes of a particular TEAE, all episodes will be counted in the summary table.

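### The causality scale allows Possibly Related only for a known or expected response pattern, so an unanticipated reaction, read literally, meets none of the three listed halting rules

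*Protocol*

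**What the plan says.** Protocol Section 14.2.3 gives the investigator five descriptions for rating the relationship of an AE to study drug.

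- Possibly Related: reasonable timing, and the event "follows a known or expected response pattern to the suspected study drug, but that could readily have been produced by a number of other factors". This is the weakest positive rating.
- Probably Related: reasonable timing, "and that follows a known or expected response pattern to the suspected study drug. The AE could have been produced" by other factors, but these are judged not likely.
- Definitely Related: clear timing and the same kind of pattern, with the added requirement "that is confirmed by improvement on stopping and reappearance of the event on repeated exposure".
- Unlikely Related: the event could reasonably have another cause, and it is a case "where there is no known or expected response pattern to the suspected study drug".
- Not Related: clearly unrelated beyond reasonable doubt, because another cause is the most plausible, the timing does not fit, or a link is biologically implausible.

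Protocol Section 8.6.1, repeated in the Synopsis and in SAP Section 5, lists three events that pause enrolment and dosing: one SAE, three similar events of grade 3 or higher, or one AESI. Each is conditional on relatedness; the third reads "One AESI, considered at least possibly related to the IPs". On prior knowledge, Protocol Section 14.2.6 says: "In consideration of the limited safety data available on prior skin test studies, two specific AESIs have been identified". SAP 9.1 item b tabulates "the number and percentage of patients experiencing a TEAE by strongest relationship to IP", and the same section treats events rated possibly related or stronger as related.

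**The concern.** A causality scale for a new product should let an investigator say that the product cannot be ruled out when the timing fits and nothing else is known. Here the weakest positive category also asks for a pattern that is already known or expected. By the protocol's own account little safety experience exists, so few patterns can be known. The event a halting rule most needs to catch, the first reaction that nobody foresaw, is the one these descriptions do not accommodate.

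Two things are at stake. One is the automatic study-wide pause. The other is the relatedness table. SAP Sections 2.3 and 10 drop every efficacy endpoint, so safety is all that is analysed, and item b of SAP 9.1 takes the investigator's category as it stands.

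**Working it through.** The documents give no figure to reproduce. The check takes one type of event through the definitions: timing is plausible, no response pattern is known or expected, and there is no reason to call a link biologically implausible.

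**Step 1. Which categories are open?**

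| Category (14.2.3) | Needs a known or expected pattern? | Open to this event? |
|---|---|---|
| Definitely | yes | no |
| Probably | yes | no |
| Possibly | yes | no |
| Unlikely | no, but needs another reasonable cause | only if such a cause exists |
| Not Related | no, but must be clearly unrelated | only if another cause is clearly the most plausible |

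Three of five categories need the pattern. If another cause is reasonable, the event goes to Unlikely Related. If there is none, it fits no category.

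**Step 2. Which halting rules can it meet?** All 3 of 3 rules in Section 8.6.1 need Possibly Related or stronger. None of those categories is open, so the event meets 0 of 3.

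**Step 3. Which events are affected?**

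- Anaphylaxis and immediate hypersensitivity: Sections 5.4 and 14.2.6 anticipate them. They can be read as expected patterns and can still trigger the rules.
- Rash, blistering and necrosis: Section 7.1 and the Synopsis call these unexpected and set them apart from redness and swelling. Section 14.3.1 gives them as examples of events usually considered serious. The protocol thus names events that are usually serious and, by its own label, not expected.
- Enhanced disease: pre-specified as an AESI, but no response pattern to TNX-2100 is described. Whether it counts as expected is left open.

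**Step 4. Can Definitely Related be reached?** All injections are given on Day 1, so no continuing treatment can be stopped. Section 10.4 does re-expose subjects: Stage 2 gives the same three products undiluted after 60 minutes, but only if Stage 1 caused no systemic or unusual local reaction. Section 5.3 says a DTH reaction is usually detectable at 18 hours, well after Stage 2. Only an ordinary, early local reaction could fade and reappear, so the category is practically unreachable.

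**Step 5. Scale, under assumed rates.** The documents give no rate for an unanticipated reaction. The chance of at least one case in 90 subjects is 1 − (1 − p)^90:

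- p = 1%: 1 − 0.99^90 = 60%
- p = 2%: 1 − 0.98^90 = 84%
- p = 5%: 1 − 0.95^90 = 99%

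A single case matters for the SAE and AESI rules. The grade 3 rule needs three subjects; at p = 2% the chance of three or more is 1 − (0.162 + 0.298 + 0.271) = 27%.

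**The case against.** The strongest reply is that the protocol does not depend on the listed rules alone. Section 8.6.1 opens by allowing dosing to be halted for investigation, and Section 8.6 recognises that the investigator or sponsor may stop the study for any reason. The step from Stage 1 to Stage 2 carries no causality test. Section 14.3.1 sends every SAE to the sponsor within 24 hours whatever its rated cause. All AEs are listed with their relationship, so an event rated Unlikely Related stays visible. This all stands: the sponsor would see the event and could act. What is lost is the automatic pause.

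It can also be said that investigators will read an expected pattern broadly, for example by treating necrosis as an extreme DTH response. Some may. But the DTH descriptions in Sections 5.2 and 5.3 do not mention blistering or necrosis, and Section 7.1 calls them unexpected. Safety rules should not rely on sites departing from the text.

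Several stronger readings are tempting and not supported:

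- That an unexpected reaction must be rated lower. With no alternative cause, it falls in a gap; nothing tells the site to choose Unlikely Related.
- That Definitely Related is impossible for all 90 subjects. Stage 2 is a re-exposure, so impossibility is not shown. The consequence is also small, because Possibly and Probably Related meet the same rules.
- That 84% is the chance of a missed pause. It is the chance of one occurrence at an assumed 2% rate, and says nothing about seriousness or how a site would rate the event.
- That related events will be under-counted by a known amount. The direction follows from the wording; the size cannot be derived.

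**Conclusion.** The point holds for unanticipated reactions. On the literal text, 3 of 5 categories need a known or expected pattern, 3 of 3 halting rules depend on those categories, and a well-timed event without such a pattern meets none of the rules. These counts need no assumption beyond reading the descriptions as written. How often it would matter depends on an unknown event rate and on how sites apply the wording; the percentages above are illustrations only.

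A reader might infer that the halting rules are ineffective in general. They are not: they still work for allergic reactions, the discretionary routes remain, and for enhanced disease the documents leave the matter unclear without closing it. The defect is a gap in the definitions at the place where a first-experience safety study most needs cover, and it carries into the relatedness table in SAP 9.1.

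**What to change.** In Protocol Section 14.2.3:

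- Remove the known-pattern condition from Possibly Related, so that it rests on reasonable timing where the product cannot be excluded as a cause. The condition may stay under Probably Related, since Possibly Related would then be open to an event without a known pattern.
- Define Unlikely Related by a more plausible alternative cause or implausible timing, and no longer by the absence of a known pattern. Keep it distinct in degree from Not Related, which already covers events that are unrelated beyond reasonable doubt.
- Drop the condition on stopping and re-exposure from Definitely Related.

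The sponsor should also reconcile Section 14.2.3 with Section 7.1 (unexpected findings), Section 14.3.1 (the same findings as usually serious) and Section 8.6.1 with SAP Section 5, and state how an event that fits no category is handled. No halting rule is proposed here. SAP 9.1 should say how such an event appears in item b, for instance in its own row.

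SAP Section 2.3 shows that induration outcomes were already known when that text was written, so dosing may be well advanced. In that case, a documented re-review of well-timed SAEs, AESIs and grade 3 or higher events rated Unlikely Related, or left without a category, would still serve the relatedness table.

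The cost is wording in one protocol section, a CRF completion note and IRB approval of the amendment. The downside is that somewhat more AEs will be classed as possibly related, so the related-AE rate becomes slightly less favourable.

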#### **14.2.4 Local Adverse Event by 7-point Likert Scale**

The subject self-reported severity of local AEs will be graded by the subject using a 7-point Likert scale. The scale will assess the subjects' evaluation of severity of erythema (redness), pain, pruritis and swelling following the intradermal injection.

Full details can be found in [Appendix 3](#).

#### 14.2.5      Toxicity Assessment Scales

Clinically significant symptoms and other adverse events will be assessed and graded by the Investigator as defined in the FDA guidance for industry: “Toxicity Grading Scale for Healthy Adult and Adolescent Volunteers Enrolled in Preventive Vaccine Clinical Trials” using a 4-point system (Grade 1 = mild, Grade 2 = moderate, Grade 3 = severe, and Grade 4 = potentially life threatening) (Table 8).

**Table 8:      Tables for Clinical Abnormalities (FDA, 2007)**

Vital Signs *	Mild (Grade 1)	Moderate (Grade 2)	Severe (Grade 3)	Potentially Life Threatening (Grade 4)
Fever (°C) ** (°F) **	38.0 – 38.4 100.4 – 101.1	38.5 – 38.9 101.2 – 102.0	39.0 – 40 102.1 – 104	> 40 > 104
Tachycardia - beats per minute	101 – 115	116 – 130	> 130	ER visit or hospitalization for arrhythmia
Bradycardia - beats per minute***	50 – 54	45 – 49	< 45	ER visit or hospitalization for arrhythmia
Hypertension (systolic) - mm Hg	141 – 150	151 – 155	> 155	ER visit or hospitalization for malignant hypertension
Hypertension (diastolic) - mm Hg	91 – 95	96 – 100	> 100	ER visit or hospitalization for malignant hypertension
Hypotension (systolic) – mm Hg	85 – 89	80 – 84	< 80	ER visit or hospitalization for hypotensive shock
Respiratory Rate – breaths per minute	17 – 20	21 – 25	> 25	Intubation

\* Subject should be at rest for all vital sign measurements.

\*\* Oral temperature; no recent hot or cold beverages or smoking.

\*\*\* When resting heart rate is between 60 – 100 beats per minute. Use clinical judgement when characterizing bradycardia among some healthy subject populations, for example, conditioned athletes.

Systemic (General)	Mild (Grade 1)	Moderate (Grade 2)	Severe (Grade 3)	Potentially Life Threatening (Grade 4)
Nausea/vomiting	No interference with activity or 1 – 2 episodes/24 hours	Some interference with activity or > 2 episodes/24 hours	Prevents daily activity, requires outpatient IV hydration	ER visit or hospitalization for hypotensive shock
Diarrhea	2 – 3 loose stools or < 400 gms/24 hours	4 – 5 stools or 400 – 800 gms/24 hours	6 or more watery stools or > 800gms/24 hours or requires outpatient IV hydration	ER visit or hospitalization
Headache	No interference with activity	Repeated use of non-narcotic pain reliever > 24 hours or some interference with activity	Significant; any use of narcotic pain reliever or prevents daily activity	ER visit or hospitalization
Fatigue	No interference with activity	Some interference with activity	Significant; prevents daily activity	ER visit or hospitalization
Myalgia	No interference with activity	Some interference with activity	Significant; prevents daily activity	ER visit or hospitalization
Illness or clinical adverse event (as defined according to applicable regulations)	No interference with activity	Some interference with activity not requiring medical intervention	Prevents daily activity and requires medical intervention	ER visit or hospitalization

Local AEs will be graded as described in [Section 14.2.4](#). Adverse events of systemic allergic reaction will be graded according to the World Allergy Organization Grading Scale for Systemic Allergic Reactions (see [Appendix 1](#)).

#### 14.2.6 Adverse Events of Special Interest

In consideration of the limited safety data available on prior skin test studies, two specific AESIs have been identified:

- Anaphylactic reaction ([Appendix 4](#)).
- Enhanced disease from repeated exposure to SARS-CoV-2 (in subjects who have recovered from SARS-CoV-2 infection or in subjects recently vaccinated against SARS-CoV-2).

Adverse events of special interest are events of scientific and medical interest specific to the further understanding of the TNX-2100 skin test. Investigators are advised to monitor subjects carefully for potential development of these adverse events as well as other adverse events (eg. local site reaction) and are required to have the appropriate safety equipment on site (crash cart and adrenaline auto-injectors [EpiPen, Jext or Emerade]). All investigative site staff will be trained in

identifying anaphylaxis and a medically licensed professional trained in the clinical management of anaphylaxis will be present at the skin test administration visit (Visit 1, Day 1) for the duration of Stages 1 and 2. Investigators are required to communicate such events immediately to the Sponsor. An AESI can be serious or non-serious. All AESIs should be entered in the Electronic Data Capture (EDC) within 24 hours of reported onset and will be recorded in the CRF. Serious AESIs will be recorded and reported as per [Section 14.3.1](#).

## **14.3 Serious Adverse Events and Serious Adverse Drug Reactions**

A serious adverse event (SAE; experience) or reaction is any untoward medical occurrence that, at any dose:

- Results in death;
- Is life-threatening;
- Requires in-patient hospitalization or prolongation of existing hospitalization;
- Results in persistent or significant disability/incapacity;
- Is a congenital anomaly/birth defect, or;
- Is an important medical event.

*NOTE:* The term “life-threatening” in the definition of “serious” refers to an event in which the subject was at risk of death at the time of the event. It does not refer to an event that hypothetically might have caused death if it were more severe.

### **14.3.1 Reporting of Serious Adverse Events**

The investigative site is required to report any SAE within 24 hours of becoming aware of the event, directly to Premier PV using the contact information provided in the protocol. Premier PV will confirm the receipt of any formally submitted information regarding a reportable event to the sender within one business day by email. Premier Pharmacovigilance will document and archive the appropriate receipt confirmation sent to the sender.

Events that are subject to immediate notification (within 24 hours of knowledge by any investigational site personnel) include the following:

- Serious AE (whether or not deemed drug-related or expected);
- AESI as specified in the protocol, i.e., anaphylactic reaction, and enhanced disease from repeated exposure to SARS-CoV-2 (in subjects who have recovered from SARS-CoV-2 infection or in subjects recently vaccinated against SARS-CoV-2).

Note an AESI can be serious or non-serious. (see [Section 14.2.6](#)).

- Pregnancy.

Any SAE that occurs at any time during the study, including a clinically significantly abnormal laboratory test result that is considered serious, must be reported to the Sponsor or its designee(s) so that the Sponsor may comply with regulatory obligations. If the SAE is life-threatening or fatal, it must be reported to the Sponsor or its designee(s) immediately, by facsimile and telephone. For these and all other SAEs, an SAE report form must be completed and sent by facsimile or email to the Sponsor or its designee(s) within 1 working day of the site's initial awareness of the event. These requirements apply equally to all subjects, regardless of the study phase or the at-risk subject's treatment assignment or dosage.

Medical and scientific judgment should be exercised in deciding whether expedited reporting is appropriate in other situations, such as important medical events that may not be immediately life-threatening or result in death or hospitalization but may jeopardize the subject or may require intervention to prevent one of the other outcomes listed in the definition above. These should also usually be considered serious. Examples of such events are intensive treatment in an emergency room, anaphylaxis requiring respiratory support, blistering, rash, or necrosis.

All SAEs have to be reported, whether or not considered causally related to the investigational product, or to the study procedure(s). All SAEs will be recorded in the CRF.

[figure not shown]
Any death occurring during the study, during the per-protocol follow-up period, or reported to the Investigator after study participation (no required post-study time limit) must be reported to the Sponsor or its designee(s) immediately, whether or not it is considered treatment-related.

If any SAE occurs in the course of the study, then Investigators or other site personnel inform the Premier PV team and Tonix Medical Monitor **within 24 hours of becoming aware of the event**.

Initial SAE reports must be followed by detailed descriptions. These should include copies of hospital case records and other documents when requested. Telephone and e-mail reports must be confirmed promptly either by facsimile or by email.

For reporting SAEs, the Sponsor's designated Medical Monitor should be called, and the relevant forms submitted to Premier Pharmacovigilance Department within 24 hours of the site's awareness of the SAE.

The contact information for the Medical Monitor is as follows:

The Investigator, or the Sponsor or designee in the case of a central Institutional Review Board (IRB), also must notify the IRB of the occurrence of the SAE, in writing, as soon as is practicable and in accordance with local law. A copy of this notification must be provided to the Sponsor or its designee.

In the event of an SAE that meets the criteria for expedited reporting, an investigational new drug (IND) Safety Report will be prepared for submission to the FDA. Emergency unblinding is not applicable as this is an open label study.

